6.7.2.2. Hypotheses and Analysis

Letting $S_{LY}(t)$ and $S_P(t)$ denote the progression free survival functions of abemaciclib + NSAI and placebo + NSAI respectively, the null hypothesis

$$H_0: S_{LY}(t) = S_P(t)$$

will be tested against the one sided alternative hypothesis

$$H_1: S_{LY}(t) > S_P(t).$$

There is 1 planned interim analysis and 1 final analysis to test these hypotheses. At each analysis, the hypotheses above will be tested using a one sided stratified log rank test, stratified by nature of disease and prior (neo)adjuvant endocrine therapy.

The interim analysis is planned to take place after approximately 189 investigator-assessed PFS events have occurred. The cumulative 1-sided type I error rate of .025 will be maintained using the following method. At the interim analysis, the nominal alpha level will be .00025. The remaining alpha will be spent at the final analysis. The resulting boundary p-value for the final analysis is dependent on the exact number of events observed at each analysis and can be calculated using the method of Slud and Wei (1982). If the two analyses are performed at exactly 189 and 240 events, then the boundary p-value at the final analysis will be .0249993.

The actual alpha spent and p-value required to reject the null hypothesis will be calculated based on the actual number of events observed at the time of each analysis using software that implements the alpha-spending scheme noted above (for example, ADDPLAN 6.0 or SAS 9.2).

If statistical significance is not declared at the interim PFS analysis, the final PFS analysis will be performed after 240 PFS events have been observed based on investigator assessment. Once statistical significance is declared at either interim analysis or the final analysis, the study will be positive based on the primary endpoint of PFS, and testing of secondary endpoints will proceed.

The interim PFS analyses will be performed by the DMC. The requirements for unblinding the sponsor at the interim analyses are found in Protocol Section 12.2.14.

6.7.2.3. Other Analyses

6.7.2.3.1. Progression-Free Survival Curves and Hazard Ratio

The Kaplan-Meier (KM) method (Kaplan and Meier 1958) will be used to estimate the PFS curve for each treatment arm. Point estimates and confidence intervals for the first quartile, median, and third quartile for the PFS curve of each arm will be estimated. The PFS rates for each arm will be compared at 4 months intervals up to 24 months using a normal approximation for the difference between the rates.

A Cox proportional hazard model (Cox 1972) stratified by nature of disease and prior (neo)adjuvant endocrine therapy with treatment as a factor will be used to estimate the HR between the two treatment arms and the corresponding CI and Wald p-value (Agresti 2002).

6.7.2.3.2. Restricted Mean Difference

The common method for describing benefit on the time scale is to calculate the difference in median event time between the two treatment arms. An alternative method for describing benefit on the time scale is to estimate the average difference between the KM curves. This corresponds to calculating the difference in the average time to event for the two treatment arms (Irwin 1949; Karrison 1997; Meier et al. 2004). Similar to the HR, this method uses all of the available information across the KM curves, but has the additional advantage of assessing benefit on the time scale.

To estimate an improvement in PFS with abemaciclib, we will follow the method of Irwin (1949) detailed in Karrison (1997) and Meier (2004) for estimating the 'difference in average PFS', which we will refer to more formally as the restricted mean difference in PFS.

The area under each KM curve will be calculated using numerical integration (trapezium rule) per Karrison and implemented in SAS using PROC LIFETEST. The difference between treatment arms and a CI for the difference will be formed.

Since the KM curve may be ill-determined beyond a certain range, or even undefined (if the longest observation is censored), for evaluation and comparison of means, the area under each KM curve will be calculated between time 0 and restriction time T, which is why this is referred to as a "restricted mean". Following the suggestion of Karrison, the restriction time T will be chosen as largest time point t such that the standard error (SE) of the survival estimate at time t

in each treatment group is no more than 0.075. For this purpose, we will use the simple, albeit conservative, formula proposed by Peto et al. (1977) for calculating the SE of $S(t)$ as

$SE(S(t)) = S(t)\sqrt{(1-S(t))/n(t)}$, where $n(t)$ is the number of patients still at risk at time t .

6.7.3. Gated Secondary Endpoint: Overall Survival

6.7.3.1. Background

Overall survival is an important secondary endpoint for this study. Statistical tests will be conducted according to the graphical method of Maurer and Bretz (2013) so as to control the overall type I error rate at 0.025 (one-sided) or equivalently, 0.05 (two-sided). The graphical approach can be characterized by first defining a set of prespecified null hypotheses that are organized graphically by providing initial alphas for each hypothesis and weights for each edge of the graph that will determine the propagation of α through the entire hypothesis-testing scheme.

The initial graph allocates all alpha to the primary endpoint of PFS. That is, OS will be tested only if PFS is significant. Following a positive PFS result, the one-sided alpha of .025 will be allocated between the VIS and ITT populations using a graphical approach, with an initial allocation of .005 for the VIS and .020 for the ITT. If the test of OS on the VIS is positive, the test of OS on the ITT will receive all the alpha (Figure JPBM.6.1). Likewise, the test of OS on the ITT is positive, the test of OS on the VIS will receive all the alpha. More details concerning the graphical approach and alpha spending across multiple analyses of OS are provided in Section 6.7.3.3.

[figure not shown]

Figure JPBM.6.1. Initial graph.

6.7.3.2. Definition

The OS time is measured from the date of randomization to the date of death from any cause. For each patient who is not known to have died as of the data-inclusion cut-off date for a particular analysis, OS will be censored for that analysis at the date of last contact prior to the data inclusion cutoff date.

6.7.3.3. Hypotheses and Analysis

Letting $S_{LY}(t)$ and $S_P(t)$ denote the survival functions of abemaciclib + NSAI and placebo + NSAI respectively, the null hypothesis

$$H_{0i}: S_{LY}(t) = S_P(t), i=0,1,$$

will be tested against the one sided alternative hypothesis

$$H_{1i}: S_{LY}(t) \geq S_P(t), i=0,1,$$

where $i=0$ represents the hypothesis in the VIS and $i=1$ represents the hypotheses in the ITT. There are 4 planned interim analyses and 1 final analysis to test the null hypotheses which will occur at the following time points:

- The interim PFS analysis (189 PFS events)
- The final PFS analysis (240 PFS events)
- Approximately 189 OS events in the ITT, regardless of the number of events in the VIS
- Approximately 252 OS events in the ITT, regardless of the number of events in the VIS
- Final OS analysis: At least 315 OS events in the ITT and at least 189 events in the VIS

At the time of the final analysis, it is likely that either ITT or the VIS will have more than the prespecified number of events. To properly control Type I error, the analysis of the population with more than the prespecified events will only use those events that occurred through the time

of the prespecified number of events. For example, if at the time of the final analysis, 196 events have been observed in the VIS, the analysis of the VIS will use only data through the date of the 189th event.

At each analysis, the hypotheses above will be tested using a one sided stratified log rank test, stratified by nature of disease and prior (neo)adjuvant endocrine therapy for the ITT, and stratified by prior (neo)adjuvant endocrine therapy for the VIS.

Following a positive PFS result, the one-sided alpha of .025 will be allocated between the VIS and ITT populations using a graphical approach, with an initial allocation of .005 for the VIS and .020 for the ITT. The cumulative 1-sided type I error rate within each population will be maintained using the Lan-Demets method. Specifically, an α -spending function corresponding to the following O'Brien-Fleming type stopping boundary will be used for these interim analyses:

$$\alpha^*(t_k) = 2 \left(1 - \Phi \left(\frac{\Phi^{-1}(1 - \alpha/2)}{\sqrt{t_k}} \right) \right)$$

Here, t_k is the information fraction at time k , Φ is the standard normal cumulative distribution function, and Φ^{-1} is the standard normal quantile function.

The total alpha to be allocated by the alpha-spending function for each hypothesis is based on the alpha at each node of the graph at the time of analysis (taking into account of potential alpha re-allocation through rejection of other hypothesis). The planned testing levels at each analysis for example scenarios are illustrated in [Table JPBM.6.2](#), and the actual alpha levels will be adjusted according to the rejection history and the alpha-spending functions based on observed number of events. The table assumes the number of OS events in the VIS is 60% of that in the ITT at any given analysis, and that 47 and 95 OS events are observed in the ITT at the time of the interim and final PFS analyses (for example, ADDPLAN 6.0 or SAS 9.2).

Test	Node α at Analysis	Nominal Significance Level				
		Interim PFS Analysis	Final PFS Analysis	189 OS events	252 OS events	Final OS analysis
1. Initial Graph						
PFS	0.025	0.00025	.0249993	n/a	n/a	n/a
2. Graph following significant PFS result						
VIS OS	0.005	1×10^{-9}	3×10^{-7}	.0003	.0016	.0045
ITT OS	0.020	2×10^{-9}	2×10^{-5}	.0027	.0085	.0171
3. Graph following significant PFS and VIS OS result						
ITT OS	0.025	7×10^{-9}	4×10^{-5}	.0038	.0110	.0211
4. Graph following significant PFS and ITT OS result						
VISC OS	0.025	7×10^{-9}	4×10^{-5}	.0038	.0110	.0211

Table JPBM.6.2. Example Nominal Significance Levels

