6.7.3.4. Other Analyses

The KM method will be used to estimate the OS curve for each treatment arm. Point estimates and CIs for the first quartile, median, and third quartile for the OS curve of each arm will be estimated. The OS rates at 1, 2, and 3 years for each arm will be estimated and compared using a normal approximation for the difference between the rates.

A stratified Cox proportional hazard model (stratified by nature of disease and prior (neo)adjuvant endocrine therapy) with treatment as a factor will be used to estimate the HR between the abemaciclib + NSAI group and the placebo + NSAI group, and the corresponding CI and Wald p-value.

A restricted mean difference analysis on OS will be conducted as described for PFS in Section [6.7.2.3.2.](#)

Follow-up time for OS will be defined from the date of randomization and will use the inverse of the censoring rules for OS. The median follow up time will be calculated using the KM method.

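### Does cutting the overrunning population back to its planned death count at the final OS test lose something the SAP should have kept?

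*SAP*

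**What the plan says.** SAP 6.7.3.3 sets one joint trigger for the last look: "Final OS analysis: At least 315 OS events in the ITT and at least 189 events in the VIS". Since the two targets will rarely be met on the same day, the SAP remarks that "it is likely that either ITT or the VIS will have more than the prespecified number of events". Its rule for the overshooting population is this: "To properly control Type I error, the analysis of the population with more than the prespecified events will only use those events that occurred" by the time the planned count was reached. The worked case begins "if at the time of the final analysis, 196 events have been observed in the VIS"; the VIS data are then cut at the date of the 189th death.

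Within each population, alpha is spent by an O'Brien-Fleming-type Lan-DeMets function, starting from 0.005 for VIS and 0.020 for ITT, and either can rise to 0.025 if the other hypothesis is rejected. Table JPBM.6.2 gives example levels. On the table's basis the SAP says "The table assumes the number of OS events in the VIS is 60% of that in the ITT at any given analysis", and on the levels finally used, "the actual alpha levels will be adjusted according to the rejection history and the alpha-spending functions based on observed number of events".

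Section 6.7.3.2 defines censoring separately for each analysis: "OS will be censored for that analysis at the date of last contact prior to the data inclusion cutoff date". Section 6.7.3.4 adds the descriptive output ("The KM method will be used to estimate the OS curve for each treatment arm", with a stratified Cox hazard ratio) and does not repeat the truncation rule.

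**The concern.** The stated reason for truncation is type I error control, and a statistician's first reaction is that spending functions already handle an unplanned event count. If cumulative spending is held at the allocated alpha once the information fraction reaches 1, and the final boundary is solved again with the true covariance, all deaths can be used at the same calendar date and the same error rate. The SAP already recalculates its levels from observed counts, so the tools are there. On that view the rule discards deaths already collected, on the gated and alpha-controlled secondary endpoint, in a situation the SAP itself calls likely.

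A second worry is reporting. Section 6.7.3.4 does not say whether the Kaplan-Meier curves and hazard ratio use the truncated or the full data, so a p-value and its hazard ratio might rest on different sets of deaths.

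**Working it through.** **Inputs from SAP 6.7.3.3 and 5.2.** Final targets 315 (ITT) and 189 (VIS); earlier looks at 47, 95, 189 and 252 ITT deaths; VIS deaths 60% of ITT; initial alphas 0.020 and 0.005, one-sided; 2:1 randomization.

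**Assumed, because the documents give no figure.** OS hazard ratios of 0.70 to 0.80, and any VIS share other than 60%.

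**Step 1: reproduce Table JPBM.6.2.** Spending is α*(t) = 2[1 − Φ(Φ⁻¹(1 − α/2)/√t)]. For ITT at 189 deaths, t = 189/315 = 0.60 and Φ⁻¹(0.99) = 2.326, so α* = 2[1 − Φ(2.326/0.775)] = 2[1 − Φ(3.003)] = 0.0027. Solving all five looks by recursive integration gives, at the last three:

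| Node alpha | 189 ITT deaths | 252 ITT deaths | Final | Table |
|---|---|---|---|---|
| 0.005 (VIS) | 0.00029 | 0.00161 | 0.00446 | .0003, .0016, .0045 |
| 0.020 (ITT) | 0.00266 | 0.00847 | 0.0171 | .0027, .0085, .0171 |
| 0.025 | 0.00379 | 0.0110 | 0.0211 | .0038, .0110, .0211 |

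The plan's figures hold.

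**Step 2: how large is the overrun?** At a 60% share, 0.60 × 315 = 189, so both targets are met together and no deaths are cut. The SAP's example has 196 VIS deaths, or t = 196/189 = 1.037. For ITT to overrun, the VIS share must fall below 60%: at 55%, 189/0.55 = 344 ITT deaths; at 50%, 189/0.50 = 378.

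**Step 3: type I error under each rule.**

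| Rule at the final look | VIS 196 deaths, node 0.005 | ITT 344 deaths, node 0.020 |
|---|---|---|
| Truncate (t = 1) | 0.00500 | 0.0200 |
| Planned boundary on all deaths | 0.00507 | 0.02076 |
| Spending formula evaluated uncapped at t > 1 (cumulative alpha) | 0.00584 | 0.0260 |
| Capped and re-solved | 0.00500 (final level 0.00438) | 0.0200 (final level 0.0162) |

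With no rule for the overrun, error exceeds the allocation. Truncation and cap-and-re-solve both restore it exactly.

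**Step 4: what the alternative gains.** The mean of Z after d deaths is −ln(HR)·√(d × 2/3 × 1/3). For ITT at HR 0.75 and 315 deaths this is 0.2877 × √70 = 2.407, against a critical value of 2.119. The last look alone then gives Φ(0.288) = 61%, and 62.7% once the earlier looks are counted. At 344 deaths the mean is 0.2877 × √76.4 = 2.515 against 2.140: Φ(0.375) = 65%, and 66.2% with earlier looks.

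| Case | HR | Truncated | All deaths, re-solved | Gain (points) |
|---|---|---|---|---|
| 60% share (no overrun) | any | – | – | 0 |
| VIS 196 (SAP example) | 0.70 | 38.9% | 40.4% | 1.5 |
| VIS 196 | 0.75 | 23.4% | 24.3% | 0.9 |
| VIS 196 | 0.80 | 12.7% | 13.2% | 0.5 |
| ITT 344 (assumed 55% share) | 0.75 | 62.7% | 66.2% | 3.5 |
| ITT 378 (assumed 50% share) | 0.75 | 62.7% | 70.0% | 7.2 |

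The VIS rows keep the 60% share at the interim looks.

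**Step 5: what the alternative can lose.** Suppose the hazard ratio is as stated up to the truncation date and 1.0 afterwards. For ITT 344 at HR 0.75 the mean of Z falls to 2.407 × √(315/344) = 2.303 against the stricter 2.140: Φ(0.163) = 56%, and 59.7% with earlier looks, against 62.7% truncated. For VIS 196 at HR 0.70 power is 37.5% against 38.9%. The two rules break even at a late hazard ratio of about 0.87 (ITT 344, HR 0.75) or 0.84 (VIS 196, HR 0.70). On the log scale the late effect must keep a little under half its earlier size: ln 0.87/ln 0.75 = 0.48 and ln 0.84/ln 0.70 = 0.49.

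**Step 6: which data the hazard ratio uses.** Section 6.7.3.3 words its rule in terms of the analysis of the population, and its example restricts the data themselves, not only the log-rank statistic. Section 6.7.3.2 ties censoring to the cutoff for the particular analysis. Read together, an overrunning population has its own cutoff date at the final analysis, and the hazard ratio and curves that accompany its test follow that date.

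**The case for a change.** The best case for a change is that truncation is sufficient but not necessary. Cap-and-re-solve holds the error at the allocated alpha; simulation of both populations under the global null gives a familywise rate of 0.0216 to 0.0225 for VIS shares of 50% to 70%. It needs no further data or follow-up, and under proportional hazards it never has less power. All of that stands.

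It does not make the SAP wrong. The SAP says truncation controls type I error, which is true, and does not claim that no other method could. The larger gains depend on VIS shares of 55% or 50% that the documents do not give; the SAP says an overrun is likely but not how large. Proportional hazards cannot be taken for granted either: SAP 6.7.5.2 plans for follow-up treatment with another CDK4/6 inhibitor affecting survival, which could weaken the late effect. Truncation also makes the overrunning population's test insensitive to when the cutoff is called. That has some value here, since 6.14.2 leaves the later OS analyses to the sponsor.

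On reporting, a cross-reference in 6.7.3.4 would be tidy. Its absence is unstated detail, and a mismatch between p-value and hazard ratio is conjecture.

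Two clerical points nearby are real but separate. Section 6.14.2 counts three OS interim analyses where 6.7.3.3 lists four. The first VIS entry in Table JPBM.6.2, 1×10⁻⁹, comes out at about 4×10⁻¹³ from the SAP's formula. That entry is one of a set of example levels to be recalculated from observed deaths, and neither point bears on the truncation rule or alters a result.

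**Conclusion.** The concern does not hold. The rule is prespecified, the final levels it relies on reproduce, and it delivers exactly the allocated alpha of 0.005, 0.020 or 0.025. No power is lost against the planned 315 and 189 deaths. The alternative is equally valid, but it is a trade-off: no gain at the SAP's 60% share, 0.5 to 1.5 points in the SAP's own 196-death example, more only with overruns the documents do not predict, and a loss if the late log hazard ratio falls below a little under half its earlier size. The power figures rest on assumed hazard ratios of 0.70 to 0.80 and, for ITT, on assumed VIS shares; the type I error results do not depend on the hazard ratio. Keeping truncation is a reasonable design decision.

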6.1. General Considerations

6.1.1. Populations

The **entered** population includes all patients who sign the informed consent document.

The **enrolled** or **intent-to-treat (ITT)** population includes all randomized patients.

The **visceral disease (VIS)** population includes all randomized patients with visceral disease at baseline as per CRF.

The **randomized and treated (RT)** population includes all randomized patients who received at least one dose of abemaciclib, placebo, or NSAID.

Unless otherwise noted, all disposition analyses will be performed on the entered population, all patient characteristic and efficacy analyses will be performed on the ITT population, and all safety and exposure analyses will be performed on the RT population. An alpha controlled OS analysis will be performed on the VIS population.

All analyses will be performed by treatment arm. Unless otherwise noted, all analyses on the ITT population will be performed by assigned treatment arm and all analyses on the RT population will be performed by actual treatment received.

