6.7. Efficacy Analyses

6.7.1. General Considerations

6.7.1.1. Population

Unless otherwise noted, all efficacy analyses will be performed on the ITT population.

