6.7.1.2. Stratification Factors

The stratification factors for the analysis of primary and secondary analyses are:

- nature of disease (visceral metastases vs bone only metastases vs other)
- prior (neo)adjuvant endocrine therapy (aromatase inhibitor vs other vs none).

The stratification factors are captured in the IWRS and on electronic clinical (case) report forms (eCRFs). Unless otherwise specified, all stratified analyses will be based on the stratification factors per IWRS. A cross tabulation of the frequency of each level of each stratification factor per IWRS and eCRF will be produced.

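### Does the final overall survival analysis leave the visceral-disease (VIS) test without a matching hazard ratio, interval and curve on a defined data cut?

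*SAP*

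**What the plan says.** After a positive PFS result, SAP 6.7.3.3 splits the one-sided 0.025 into 0.005 for OS in VIS and 0.020 for OS in ITT. The final OS analysis needs both event targets, 315 in ITT and 189 in VIS. The section expects one population to overshoot and handles it so: "To properly control Type I error, the analysis of the population with more than the prespecified events will only use those events" that occurred up to its target. With 196 VIS deaths, for example, "the analysis of the VIS will use only data through the date of the 189th event". The ITT log-rank test is stratified by both randomization factors, the VIS test by prior endocrine therapy only.

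Other sections that bear on the estimates:

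- 6.7.3.2 sets censoring by analysis: "OS will be censored for that analysis at the date of last contact prior to the data inclusion cutoff date".
- 6.7.3.4 plans Kaplan-Meier curves, quartiles, 1-, 2- and 3-year rates, a restricted mean difference, and "A stratified Cox proportional hazard model (stratified by nature of disease and prior (neo)adjuvant endocrine therapy) with treatment as a factor". It names neither a cut nor VIS.
- 6.7.1.1 sets the default: "Unless otherwise noted, all efficacy analyses will be performed on the ITT population". Section 6.1.1 adds that "An alpha controlled OS analysis will be performed on the VIS population", and defines VIS as the set that "includes all randomized patients with visceral disease at baseline as per CRF".
- 6.7.1.2 says that, unless otherwise specified, "all stratified analyses will be based on the stratification factors per IWRS". It also plans a cross-tabulation of each factor as recorded in IWRS and on the eCRF.
- 6.12 plans OS subgroup analyses for every stratification factor, with within-subgroup hazard ratios and intervals in a forest plot. Visceral metastases is one level of nature of disease.

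**The concern.** VIS OS is one of only two alpha-controlled hypotheses after PFS, and a win there passes its alpha to ITT. A reader will want a hazard ratio, interval and curve from the same patients, deaths and strata as the p-value. Read narrowly, the SAP does not promise them.

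- The truncation is justified by type I error, which concerns the test, and 6.7.3.4 does not repeat it for the estimates.
- With ITT as the default population and nature of disease in the Cox strata, 6.7.3.4 reads as if written for ITT alone.
- The visceral row in 6.12 could include deaths after the 189th, and it could be built from IWRS rather than the CRF.

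At stake would be a p-value and hazard ratio that do not correspond, and a choice of cut made once the results are known.

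**Working it through.** **The plan's own figures.** With the spending function in 6.7.3.3 and looks at 47, 95, 189, 252 and 315 of 315 deaths, recursive integration gives final nominal levels of 0.00446 (alpha 0.005), 0.0171 (0.020) and 0.0211 (0.025). Table JPBM.6.2 prints .0045, .0171 and .0211. The 189- and 252-death columns also agree. One early cell does not: VIS at the interim PFS analysis computes to about 3.7 × 10⁻¹³ against a printed 1 × 10⁻⁹. That has no bearing on the final cut.

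**How often the cuts differ.** The table assumes that VIS supplies 60% of deaths, and 0.60 × 315 = 189. The number of VIS deaths at the 315th ITT death still varies by chance.

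- Binomial(315, 0.6): SD 8.7, and P(exactly 189) = 0.046. Mean overshoot is 7.2 VIS deaths or, when VIS falls short, 12.1 ITT deaths.
- Hypergeometric (assuming 270 of 450 patients visceral): SD 4.8, and P(exactly 189) = 0.084. Mean overshoot is 4.1 VIS or 6.9 ITT deaths.

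One population is therefore truncated, sometimes by a single death, in about 92 to 95% of trials. The SAP itself calls this likely.

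**How far the estimate moves.** With 2:1 allocation, SE(log HR) = √(4.5/D). For nested cuts at D₁ < D₂ deaths, the SD of the change in log HR is √(4.5(1/D₁ − 1/D₂)). Relative to the SE at D₁ this is √(1 − D₁/D₂). The documents give no OS hazard ratio, so 0.75 is an assumption.

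| Cuts compared | SD of change | SE at the test's cut | Ratio | 0.75 moves within (95%) | 95% CI around 0.75 |
|---|---|---|---|---|---|
| VIS 189 vs 196 (SAP example) | 0.029 | 0.154 | 19% | 0.71–0.79 | 0.55–1.01 |
| ITT 315 vs 327 (mean binomial overshoot) | 0.023 | 0.120 | 19% | 0.72–0.78 | 0.59–0.95 |
| ITT 315 vs 344 (VIS share 55%: 189/0.55) | 0.035 | 0.120 | 29% | 0.70–0.80 | 0.59–0.95 |
| VIS 189 vs 205 (VIS share 65%: 0.65 × 315) | 0.043 | 0.154 | 28% | 0.69–0.82 | 0.55–1.01 |

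In every row the movement stays inside the interval that would be printed beside the estimate.

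**Strata.** VIS is a visceral-only set per CRF, so nature of disease per CRF is constant within it. The Cox model of 6.7.3.4 then reduces to stratification by prior endocrine therapy, as in the VIS log-rank test. With IWRS strata the two differ only through patients whose IWRS and CRF entries disagree. The documents give no rate for that, and the planned cross-tabulation will show it.

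**Reading the sections together.** Section 6.7.3.3 speaks of the analysis and of data, in terms wider than the log-rank statistic. Section 6.7.3.2 attaches the cutoff to a particular analysis, so two cutoffs at one look are consistent with it. The looks at 189 and 252 ITT deaths have one trigger and no truncation, so the question of the cut arises only at the final look.

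**The case for a change.** The strongest counter-argument does not depend on overshoot. At all five OS looks the VIS test has no estimate expressly assigned to it, no Kaplan-Meier curve is named for VIS, and the 6.12 row is tied neither to the CRF definition nor to the 189-death cut. That is a fair description of the text. The alpha split came in with SAP Version 5, and 6.7.3.4 appears not to have been revised to match.

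It can also be said that the choice of cut could change the apparent verdict. With bivariate normal statistics of correlation √(D₁/D₂) and drift −ln(HR)·√(2D/9), the two cuts fall on opposite sides of the final boundary as follows, at assumed hazard ratios of 0.70, 0.75 and 0.80:

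- VIS 189 vs 196, boundary .0045: 6.0, 4.7 and 3.1%.
- ITT 315 vs 327, boundary .0171: 4.3, 6.0 and 6.1%.
- ITT 315 vs 344, boundary .0171: 6.7, 9.4 and 9.5%.

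With no effect, each is below 1%. These figures are right, but they describe a comparison the SAP does not make. The test is the log-rank test on the truncated cut, fixed in advance, and no rule sets the Cox Wald p-value against .0045 or .0171. What stands is that the write-up of descriptive VIS results is thinner than it could be.

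**Conclusion.** No change is needed. The tests, their cuts, the boundaries and the alpha flow are all specified, and no choice of descriptive cut can alter the prespecified p-value. What is missing is detail about descriptive output, and analysts would normally fill it by reporting the VIS hazard ratio, interval and curve on the VIS test's own cut and strata, as the wording of 6.7.3.3 already suggests. A hazard ratio and interval for visceral disease is in any case planned in 6.12.

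For the SAP's own example the effect of the cut is a log hazard ratio shift with SD 0.029, about 19% of the standard error. It rises to 28 or 29% if the VIS share of deaths is 65% or 55%. These sizes rest on 2:1 allocation, the usual event-based variance and an assumed hazard ratio of 0.75. The effect of IWRS and CRF disagreement cannot be sized from the documents.
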